3.5.3.2 Telephone Call 2 Days after Repeat SP-102 Injection

The subject should be contacted 2 days \pm 1 day after the repeat SP-102 injection. The following

[REDACTED]

[figure not shown]
3.5.5 Assessments for Early Termination

If the subject's participation in the study is terminated prematurely for any reason, the reason for such ET should be documented and the W24 (D169) procedures should be performed. If the ET occurs prior to W4 (D29), the subject should be encouraged to continue in the study until W4 (D29), if possible. In case of ET, the subject should be encouraged to return to the site for ET procedures, or failing a return visit, a telephonic visit should be arranged to encourage the subject to complete the W24 (D169) procedures (Section 3.5.2.11).

An EOS eCRF page should be completed for every subject who receives IP, whether the subject completes the study or not. The reason for any ET should be indicated on this form. The primary reason for the ET should be selected as noted in Section 3.3.3.

3.5.6 Efficacy Assessments

Medical advisors, psychometricians, and clinical research associates (CRAs) may request to review subject evaluations occurring as part of this protocol. A site and subject rater training program and a surveillance mechanism for protocol outcome measures will be implemented and described in separate operational plans. Site raters will receive didactic scale trainings and placebo response training either by webinar or through a designated study web portal. A subject training video, specific to the subject reported outcome measures in this protocol and placebo response training, will be provided to all study subjects for review and completion. The data surveillance program to be implemented will be specific to identified data flags, to be reviewed on a regular basis for identification of potential scoring anomalies and variability. The data surveillance program to be implemented will be specific to identified data flags, to be reviewed on a regular basis by a reviewer (blinded to treatment arm) for identification of potential scoring anomalies and variability. If clinically significant anomalies are detected on subject-rated scales, sites may be requested to show the video to the subject again for re-training.

3.5.6.1 Numeric Pain Rating Scale

The NPRS (Appendix E) is an 11-point scale (0 to 10-point scale where 0 is no pain and 10 is worst pain imaginable) that allows the subject to rate the severity of their pain intensity at various points in time (Turk-2003). Twice daily in the morning and evening (approximately 12 hours apart), the subject will use the NPRS to record their average and worst pain in the past 12 hours.

After the Screening Visit, the NPRS will be collected twice daily using the eDiary through W12; thereafter, the NPRS will be collected at clinic visits only. The eDiary

subject assignment should remain the same throughout the trial, and eDiaries should only be re-assigned for completed/withdrawn subjects. The current pain intensity “pain now” will be measured at every clinic visit and used for assessment of accuracy of pain reporting and monitoring of outlier values. Morning and afternoon pain measurements will be investigated for predictability of response.

3.5.6.2 Oswestry Disability Index

The ODI ([Appendix F](#)) is a validated questionnaire that was first published in 1980 but it was updated in 2000 ([Fairbank-1980](#), [Fairbank-2000](#)). The ODI is currently the gold standard for measuring degree of disability and estimating quality of life in a person with low back pain. The ODI is questionnaire completed by the subject which contains 10 topics concerning intensity of pain, lifting, ability to care for oneself, ability to walk, ability to sit, sexual function, ability to stand, social life, sleep quality, and ability to travel. Each topic category is followed by 6 statements describing different potential scenarios in the subject’s life relating to the topic. The subject then checks the statement which most closely resembles their situation. Each question is scored on a scale of 0-5 with the first statement being zero and indicating the least amount of disability and the last statement is scored 5 indicating most severe disability. The scores for all questions answered are summed, then multiplied by 2 to obtain the index (range 0 to 100). Zero is equated with no disability and 100 is the maximum disability possible. The ODI will be obtained at Screening, Baseline, W4, W12, and W24.

3.5.6.3 PainDETECT

PainDETECT ([Appendix G](#)) is a 7-question validated tool to determine the prevalence of neuropathic pain in individuals with lower back pain. The 7 responses are summed for a possible score ranging from 0-35. In addition to the 7 questions, subjects note the course of pain (Persistent pain with slight fluctuations; Persistent pain with pain attacks, Pain attacks without pain between them; Pain attacks with pain between them) for a total, overall scale score of 0-38. Since its development, 4 additional questions have been added but do not contribute to scoring. They ask the patient to rate their pain now and over the last for weeks, and to mark on a body chart if their pain is radiating to other parts of the body. *PainDETECT* will be collected at Screening, Baseline, W4, W12, and W24.

3.5.6.1 Brief Pain Inventory - Short Form

The BPI-SF ([Appendix H](#)) is a 15-item self-rating scale assessing use of medications, as well as sensory, and reactive components of pain. The BPI-SF includes items that will address components of sensory pain, including severity, location, chronicity, and degree of relief due to therapy. The BPI-SF also has items that address reactive pain components, including depression, suffering, and perceived availability of relief. Respectable reliability has been demonstrated over short intervals using test-retest correlation; worst pain, $r=0.93$; usual pain, $r=0.78$; pain now, $r=0.59$. The BPI-SF will be collected at Screening, Baseline (D1), W4, W12, and W24.

3.5.6.2 Clinical and Patient Global Impression Scales

The CGIS ([Appendix I](#)) is rated on an 8-point scale, with responses ranging of responses from 0 (not assessed) and 1 (normal) through 7 (amongst the most severely ill subjects) (to be completed prior to IP administration at the Baseline (D1) Visit). The CGIC ([Appendix I](#)) scores

range from 0 (not assessed) and 1 (very much improved) through 7 (very much worse) as determined by the trained site rater. The PGIC scores range from 1 (very much improved) through 7 (very much worse) as assessed by the subject. The CGIC and PGIC are obtained at each clinic visit following Baseline (D1).

3.5.7 Safety Assessments

3.5.7.1 Physical Examination:

A complete physical examination, including examination of general appearance, skin, neck, eyes, ears, nose, throat, heart, lungs, abdomen, lymph nodes, extremities, and musculoskeletal system, will be performed at Screening. Specific musculoskeletal examination focusing on lumbar spine and lower extremities to exclude musculoskeletal sources of the predominant pain, such as SI joints and trigger points, will be performed in standardized manner and recorded. Height (in inches without shoes) and weight (in pounds) will be recorded at Screening.

3.5.7.2 General Neurological and Targeted Neurological Examinations:

A general neurological examination will include evaluation of mental status (awareness of person, place, and time), cranial nerves, motor function and balance, sensory exam (ability to feel) and reflexes. A targeted neurological examination demonstrating findings of, focusing on signs and symptoms of lumbosacral radiculopathy, including straight leg raise test, will be performed according to the checklist (see [Appendix A](#)). Both general and targeted neurological exams are to be performed by the same trained clinician throughout the study, if possible. Training for conducting examination will be available on video. General and targeted neurological examinations will be performed at Screening, Baseline (D1), W2, W4, W12, and W24, as well as if the repeat injection is administered.

The blinded Investigator will summarize and document the MRI findings based on the Lumbar Disc Nomenclature, the clinical presentation, and the Injection Plan in the eCRF prior to Baseline (D1).

3.5.7.3 Vital Signs and Body Weight:

Vital signs will include systolic and diastolic BP and heart rate. During the usual clinic visits, the subject is to be seated for approximately 3 mins before vital signs are recorded. During the injection procedure, the vital signs will need to be collected while the subject is in prone position on the fluoroscopy table ([Appendix D](#)). Vital signs will be recorded at each clinic visit.

3.5.7.4 Electrocardiogram:

Standard 12-lead ECGs will be measured on the site machines at Screening. The ECG results will be documented in the eCRF.

3.5.7.5 Laboratory Parameters:

The following clinical laboratory tests are to be performed at Screening and W24 unless noted below:

Hematology: Hemoglobin, hematocrit, red blood cell count, WBC count (with differential [lymphocytes, neutrophils, eosinophils, basophils, and monocytes]), and platelet count.

Blood Chemistry: albumin, alkaline phosphatase, AST, ALT, direct bilirubin, total bilirubin, blood urea nitrogen, calcium, chloride, creatine kinase (Screening only), creatinine, gamma-glutamyl transferase, glucose, lactate dehydrogenase, potassium, sodium, and uric acid.

Other tests: HbA1c, HIV, hepatitis B, and hepatitis C at Screening. Coagulation tests at Screening: activated PTT, PT, and INR. Coagulation tests may be repeated prior to the index and repeat injection, if deemed necessary by the Investigator.

Urinalysis: Dipstick analysis: color, turbidity, specific gravity, pH, glucose, protein, ketones, urobilinogen, bilirubin, blood nitrate, leukocyte esterase, and microscopic examination when indicated by dipstick results.

Urine drug screen: Includes opiates, barbiturates, benzodiazepines, tricyclic antidepressants, cannabinoids, PCP, cocaine, ecstasy, and amphetamines. A urine drug screen will be obtained at Screening, Baseline (D1), W2, and W4. A urine drug screen may be repeated if deemed necessary by the Investigator.

For females of childbearing potential: Serum pregnancy test at Screening. Urine pregnancy test at Baseline (D1) and at Repeat Injection. A urine pregnancy test may be repeated if deemed necessary by the Investigator.

Laboratory samples will be analyzed by a central laboratory [REDACTED] to ensure consistent interpretation of results. Samples are to be shipped to [REDACTED], [REDACTED]. In the event of an unexplained clinically noteworthy abnormal laboratory test value, the test should be repeated immediately and followed up until it has returned to the normal range and/or an adequate explanation of the abnormality is found.

3.5.7.6 Adverse Events:

All AEs occurring after the subject signs the ICF through W24, D169 will be recorded. See [Section 4](#) for additional information.

3.5.7.7 Rescue Medication Use

[REDACTED]

3.5.8 Other Assessments

Pain Catastrophizing Scale: PCS ([Appendix K](#)) is used to assess pain as a baseline characteristic only at Screening ([Sullivan-1995](#)). It was developed to quantify a subject's pain experience by asking how they feel and what they think about when they are in pain. Items on this scale were developed from clinical and experimental research on catastrophic thinking and its relation to experience of pain. The PCS is a 13-item instrument that can be completed and scored in less than 5 mins. The PCS requires a reading level of approximately Grade 6.

Hospital Anxiety and Depression Scale: HADS ([Appendix L](#)) is commonly used to determine a subject's anxiety and depression levels. The scale is comprised of 14 items rated on a scale of 0-3; 7 items focused on anxiety symptoms and 7 items focused on depression symptoms. The HADS will be used for inclusion criteria and completed at Screening only. A score of 11-14 on either the depression or anxiety subscale is indicative of moderate symptomatology. A score of ≥ 15 on either the depression or anxiety subscale is indicative of severe symptomatology ([Snaith-1994](#), [Turk-2015](#)). Subjects with HADS scores ≥ 15 will be excluded from this study ([Zigmond-1983](#)).

3.5.9 Appropriateness of Measurements

All assessments to be used in this study are commonly used, standard measurements frequently seen in radiculopathy studies.

4 ADVERSE EVENT REPORTING

Throughout the course of the study, after signing the ICF, all AEs will be monitored and recorded on an AE eCRF, including the AE's description, start and end date, seriousness, severity, action taken, and relationship to the IP. If AEs occur, the first concern will be the safety of the study subjects. All AEs will be followed until resolved or stable and the outcome documented on the eCRF.

4.1 Definitions and Criteria

4.1.1 Adverse Events

An AE is any untoward medical occurrence in a subject or clinical investigation subject administered a pharmaceutical product and which does not necessarily have to have a causal relationship with this treatment (ICH-E2A-1996). An AE can therefore be any unfavorable and unintended sign (including an abnormal laboratory finding, for example), symptom, or disease temporally associated with the use of a medicinal product, whether considered related to the medicinal product or not.

Medical interventions such as surgeries, diagnostic procedures, and therapeutic procedures are not AEs but the action taken to treat the medical condition. They should be recorded as treatment of the AEs.

4.1.2 Serious Adverse Events

A serious adverse event (SAE) or reaction is any untoward medical occurrence that at any dose:

- Results in death
- Is life-threatening
- Requires inpatient hospitalization or prolongation of existing hospitalization
- Results in persistent or significant disability or incapacity
- Is a congenital anomaly or birth defect
- Is an important medical event (eg, intensive treatment in an emergency room or at home for allergic bronchospasm; blood dyscrasias, or convulsions that do not result in hospitalization; or development of drug dependency or drug abuse; malignancy tumors [histologically different from primary tumor])

Note: The term "life-threatening" in the definition of "serious" refers to an event in which the subject was at risk of death at the time of the event; it does not refer to an event that hypothetically might have caused death if it were more severe.

Medical and scientific judgment should be exercised in deciding whether expedited reporting is appropriate in other situations, such as important medical events that may not be immediately life-threatening or result in death or hospitalization, but may jeopardize the subject or may require intervention to prevent one of the other outcomes listed in the definition above. These should also usually be considered serious.

Examples of such events are intensive treatment in an emergency room or at home for allergic bronchospasm; blood dyscrasias, or convulsions that do not result in hospitalization; or development of drug dependency or drug abuse.

Seriousness (not severity) serves as a guide for defining regulatory reporting obligations. An SAE is not necessarily severe; eg, an overnight hospitalization for a diagnostic procedure must be reported as an SAE even though the occurrence is not medically serious. By the same token, a severe AE is not necessarily serious: nausea of several hours' duration may be rated as severe but may not be considered serious.

4.1.3 Unexpected Adverse Drug Reactions

An unexpected adverse drug reaction (ADR) is a reaction for which the nature or severity is not consistent with the applicable product information (IB, [SP102-IB-2015](#)). Until product information is amended, expedited reporting is required for additional occurrences of the reaction. Reports that add significant information on specificity or severity of a known, already documented SAE constitute unexpected events. For example, an event more specific or more severe than described in the IB would be considered "unexpected." Specific examples would be (a) acute renal failure as a labeled ADR with a subsequent new report of interstitial nephritis and (b) hepatitis with a first report of fulminant hepatitis.

Guidance on reporting AEs and SAEs is described in [Section 4.2](#).

4.1.4 Abnormal Laboratory Values

Any abnormality ([Appendix N](#)) in a laboratory value that is new in onset or which has worsened in severity or frequency from the baseline condition and meets 1 of the following criteria will be recorded on the AE pages of the eCRF:

- Requires therapeutic intervention or diagnostic tests
- Leads to discontinuation of IP
- Has accompanying or inducing symptoms or signs
- Is judged by the investigator as clinically significant

4.1.5 Assessing Intensity and Relationship

All AEs will be assessed on 2 descriptive parameters: intensity and relationship to the IP:

- Intensity refers to the severity of an event and references impact on a subject's functioning.
- Relationship refers to the likelihood that the event being assessed was caused by the IP.

Intensity

Each AE will be classified according to [Appendix N](#).

When changes in the intensity of an AE occur more frequently than once a day, the maximum intensity for the experience should be noted. If the intensity category changes over a number of days, those changes should be recorded separately (with distinct onset dates).

Relationship

Each AE will be assessed as to its relationship to the IP, based on the following criteria. Although the attribution by the investigator will be collected for reported events, for analytic purposes a temporal association with the use of the IP will be assumed sufficient for at least plausible association.

Investigators are required to assess the causal relationship (ie, whether there is reasonable possibility that the study drug caused the event) using the following definitions:

- Unrelated: A clinical event, including laboratory test abnormality, with a temporal relationship to study drug administration that makes a causal relationship improbable, and/or in which other drugs, chemicals or underlying disease provide plausible explanations of the event.
- Possibly Related: A clinical event, including laboratory test abnormality, with a reasonable time sequence to administration of the study drug, but that could also be explained by concurrent disease or other drugs or chemicals. Information on study drug causality may be lacking or unclear.
- Probably Related: A clinical event, including laboratory test abnormality, with a reasonable time sequence to administration of the study drug, unlikely to be attributed to concurrent disease or other drugs or chemicals, and that follows a clinically reasonable response on re- administration (rechallenge) or withdrawal (dechallenge) of the study drug.
- Definitely Related: A clinical event, including laboratory test abnormality, with a temporal relationship to study drug administration that makes a causal relationship definite and is clearly related to use of the IP.

When assessing the relationship to the IP, the following criteria will be considered:

- Positive rechallenge
- Positive dechallenge (resolution upon stopping suspect the IP, in absence of other intervention or treatment)
- Known class effect
- Biological plausibility
- Lack of alternative explanation—concomitant drug or disease

4.2 Reporting Procedures and Requirements

4.2.1 Adverse Events

AEs occurring after the subject signs the ICF until the 30 days after the last study visit will be recorded. Any AEs occurring before the start of treatment (ie, before the first dose of the IP) will be recorded in the medical history. Also, the sign, symptom, or disease present before starting the treatment period are only considered AEs if they worsen after starting the treatment period.

If a subject has new or worsening pain, or onset of new neurological symptoms, a follow-up MRI may be obtained after consultation with the Medical Monitor.

If the investigator detects an AE in a study subject within 30 days after the last scheduled follow-up visit and considers the event possibly related or related to prior study treatment, the investigator should report it to the sponsor [REDACTED]

The investigator should report all AEs on the AE page(s) of the eCRF and source documents (if the eCRF is unavailable for direct data entry [DDE]), regardless of seriousness, severity, and causality. Whenever possible, an AE will be reported using a diagnostic term, (eg, “common cold” or “upper respiratory infection” rather than “runny nose, cough, mild fever”) and should be described with the attributes described in [Section 4.1.5](#).

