[REDACTED] Eligible subjects will then be randomly assigned (in a 1:1 ratio) on D1 to receive a single dose of an SP-102 TF, or placebo [REDACTED] in the vicinity of the epidural space or [REDACTED] under fluoroscopic guidance (for instructions on study drug injection see [Appendix D](#)). This first injection is referred to as the “index injection”. An appropriately trained physician, hereafter called the Injection Physician, administering the DB investigational product (IP) and other assisting staff (eg, nurse) will, therefore, not be blinded to the treatment assignment, while the rest of study staff involved in assessments and collection of data will remain blinded. Procedures will be in place at each site to ensure blinding, minimizing personnel involved with injection, and guarantee sequestration of imaging data acquired at the time of injection.

Fluoroscopic imaging guidance is required by this protocol to ensure proper placement of the injection needle (see instructions in [Appendix D](#)). Long-term persistent AEs are rarely seen with fluoroscopically-guided lumbosacral TF injections, however immediate and delayed AEs may include vasovagal episodes, procedure interruption from intravascular flow, pain exacerbation, injection site soreness, headache, and insomnia ([Plastaras-2015](#)). Avoidance of risk of procedural AEs in the placebo group by implementing an [REDACTED]

[REDACTED] is consistent with ethical considerations and use of [REDACTED] in interventional/surgical clinical trials (Wartolowska-2014). In addition to safety considerations and lowering the risk of procedural complication in the control group, the choice of an [REDACTED]

The choice of the TF injection approach with direct deposition of drug near the ventral epidural space at the affected level is selected based on published reviews documenting better effectiveness as compared to other approaches. For lumbar disc herniation with unilateral symptoms, the evidence for analgesic effect and ability to prevent surgery is greater for TF epidural injections as compared to caudal or interlaminar approaches (Manchikanti-2012; Cohen-2013).

[figure not shown]

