3.3.4 Removal of Subjects from Therapy or Assessment

A subject will be considered to have completed the study when he or she completes the W24 (D169) visit. If a subject is discontinued at any time after randomization into the study, the investigator will make every effort to follow the subject and complete the End of Study (EOS)/Early Termination (ET) assessments as shown in [Section 3.5.1](#). Sufficient subjects will be enrolled such that 332 subjects complete the study through W4.

A termination electronic case report form (eCRF) page should be completed for every subject who receives IP, whether the subject completes the study or not. The reason for any early discontinuation should be indicated on this form. The primary reason for a subject discontinuing early should be selected from the following standard categories of ET:

- *Adverse Event*: Clinical or laboratory events occurred that, in the medical judgment of the investigator for the best interest of the subject, are grounds for discontinuation. This includes serious, nonserious AEs and AESI regardless of relation to the IP.
- *Death*: The subject died.
- *Withdrawal of Consent*: The subject desired to withdraw from further participation in the study in the absence of an investigator-determined medical need to withdraw. If the subject gave a reason for withdrawing, it should be recorded in the eCRF.
- *Protocol Violation*: The subject's findings or conduct failed to meet the protocol entry criteria or failed to adhere to the protocol requirements (eg, drug noncompliance, failure to return for defined number of visits). The violation necessitated early discontinued from the study.
- *Lost to Follow-Up*: The subject stopped coming for visits and study personnel were unable to contact the subject.
- *Other*: The subject was discontinued for a reason other than those listed above, such as theft, loss of IP, or termination of study by sponsor.

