3.4 Treatments

3.4.1 Details of Study Treatments

Information about the IPs is provided in [Table 3.1](#).

Table 3.1: Details of Investigational Products

	SP-102	Placebo
Ingredient	[REDACTED]	
Manufacturer	[REDACTED]	
Dose(s)	[REDACTED]	
Route	[REDACTED]	
Formulation	[REDACTED]	
Strength(s)	[REDACTED]	

SP-102 drug product is comprised of [REDACTED]

The drug product is a sterile [REDACTED]

[REDACTED] which is intended to be delivered via a TF injection, using 6-inch long extension tubing. The placebo, [REDACTED]

[REDACTED]. While the drug is sterile manufactured and is sterile for injection, the outside of the syringes is not sterile; thus, attachment of the syringe and IP injection should be the last step prior to removal of needle and finishing the procedure.

Under Good Manufacturing Practices, SP-102 was manufactured by [REDACTED]. All IP will be kept in a locked area with limited access. [REDACTED]

[REDACTED] Deviations of storage temperature outside this range should be documented and Semnur or designee should be promptly notified. IP kits should not be frozen. If any component of the IP kit is damaged, Semnur or designee must be notified as soon as possible.

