5.2.9.1 Adverse Events

All AEs will be coded using the most current version of MedDRA.

The incidence of treatment-emergent AEs (TEAEs) (number and percent of subjects reporting the AE at least once during the study), SAEs, AEs related to study treatment, SAEs related to treatment, and AEs leading to study discontinuation will be summarized by treatment.

A TEAE is defined as any AE that has an onset on or after the dose of IP, or any pre-existing condition that has worsened on or after the first dose of IP.

The incidence of TEAEs and treatment-related AEs will also be summarized by maximum severity and most-related relationship to IP by MedDRA primary system organ class and preferred term. The summary will include the total number and percentage of subjects reporting an event. In counting the number of events reported, a continuous event, ie, reported more than once and which did not cease, will be counted only once; non-continuous AEs reported several times by the same subject will be counted as multiple events.

Any TEAEs will be summarized by treatment group, for each post-randomization treatment period:

- Occurring after the randomization injection, but prior to a second injection (of SP-102)
- Occurring after the second injection (of SP-102)

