### 7.2.2 Safety Analysis Population

This is defined as all randomized subjects who received an index injection (study drug). For safety analyses, subjects will be grouped based upon the treatment received (even if different from what they were randomized to).

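### AE rules are anchored to the dose, not the start of the injection procedure, so events at needle placement and procedures stopped before dosing can miss every AE summary table

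*Protocol*

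**What the plan says.** **Recording.** Protocol 4.2.1 says: "Any AEs occurring before the start of treatment (ie, before the first dose of the IP) will be recorded in the medical history". Protocol 4 says: "after signing the ICF, all AEs will be monitored and recorded on an AE eCRF". Protocol 3.5.7.6 says: "All AEs occurring after the subject signs the ICF through W24, D169 will be recorded". Protocol 3.4.8.1 treats illnesses first occurring during the study as AEs for the eCRF. The last paragraph of Protocol 4.2.1 sends all AEs to the AE page, whatever their seriousness, severity or causality.

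**Order of the procedure.** Protocol 3.4.1 says that "attachment of the syringe and IP injection should be the last step prior to removal of needle and finishing the procedure". Randomisation has already taken place by then (Protocol 3.1 and 3.4.3).

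**Known events.** Protocol 3.1 says of transforaminal injections that "immediate and delayed AEs may include vasovagal episodes, procedure interruption from intravascular flow, pain exacerbation". It justifies the control partly by sparing the placebo group procedural risk.

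**Analysis.** Protocol 5.2.9.1 states: "A TEAE is defined as any AE that has an onset on or after the dose of IP". It adds pre-existing conditions that worsen from that point, and SAP 7.13.1 uses the same anchor. Protocol 5.2.5 and SAP 7.2.2 limit the Safety Population to randomised subjects who received the injection, and SAP 7.13 runs all safety analyses on it. SAP 7.13.1 plans separate tables of study-procedure-related TEAEs.

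**Termination page.** Protocol 3.3.4 says: "A termination electronic case report form (eCRF) page should be completed for every subject who receives IP". Protocol 3.5.5 words the end-of-study page the same way.

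**The concern.** Needle placement comes after randomisation but before the drug, and the AE rules begin at the drug. The plan means to count procedure-related harm, and the protocol names events that can occur during placement, such as a vasovagal episode or an interruption for intravascular flow. If the pre-dose part of the procedure is cut off, the procedure-related tables are incomplete for the route under test.

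The two routes differ, transforaminal for SP-102 and intramuscular for placebo. On the protocol's own reasoning, the omitted events would come mainly from SP-102 subjects, so the between-arm AE comparison could look somewhat better for SP-102 than it should. A secondary objective is the safety of the transforaminal injection itself.

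**Working it through.** The documents state no figure for this point. The check is therefore a comparison of the rules, followed by an illustration of scale.

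**1. Where an event at needle placement is recorded**

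| Place | Destination |
|---|---|
| Protocol 4.2.1, pre-dose sentence | Medical history |
| Protocol 4.2.1, last paragraph | AE page |
| Protocol 4 | AE page |
| Protocol 3.5.7.6 | Recorded as an AE |
| Protocol 3.4.8.1 | AE on the eCRF |

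One sentence points one way and four points of text the other. This is a contradiction, not a settled rule.

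**2. What reaches the tables**

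| Index procedure | TEAE tables |
|---|---|
| Event after the drug | Counted |
| Event at needle placement, drug then given, event worsens after the dose | Counted |
| Event at needle placement, drug then given, no worsening, literal reading | Not counted |
| Same, but on the AE page and classified by date | Counted |
| Event at needle placement, no drug given | Not counted on any reading: outside the Safety Population |

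The date reading is possible because the AE fields listed in Protocol 4 include a start date and no clock time, and SAP 7.3.3 computes study day from dates. Neither document says which reading applies.

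**3. Scale, for illustration only**

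Input from the documents: about 400 subjects randomised 1:1 (Protocol synopsis), so 400/2 = 200 on SP-102.

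Assumptions, none from the documents:
- r = risk of an event before the drug in the transforaminal arm, 1% to 10%.
- f = share of those procedures stopped before the drug, 10% or 50%.
- q = AE incidence after the drug, 10%, whether or not there was a pre-dose event.

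Formulas:
- All started procedures, counted from procedure start: r + (1 − r)q.
- Literal rule: q. Hidden amount = r(1 − q) = 0.9r.
- Date rule, undosed subjects excluded: [r(1 − f) + (1 − r)q] / (1 − rf). Hidden amount = first line minus this.

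Example with r = 10%, f = 50%: all started = 0.10 + 0.90 × 0.10 = 19.0%. Date rule = (0.05 + 0.09)/0.95 = 14.74%. Hidden = 4.26 points.

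| r | Pre-dose events in 200 | All started | Literal table | Hidden, literal | Hidden, date, f = 10% | Hidden, date, f = 50% |
|---|---|---|---|---|---|---|
| 1% | 2 | 10.9% | 10.0% | 0.9 | 0.09 | 0.45 |
| 2% | 4 | 11.8% | 10.0% | 1.8 | 0.18 | 0.89 |
| 5% | 10 | 14.5% | 10.0% | 4.5 | 0.43 | 2.19 |
| 10% | 20 | 19.0% | 10.0% | 9.0 | 0.82 | 4.26 |

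Hidden amounts are percentage points in the SP-102 arm. If the control arm has pre-dose risk c and the same q, the net between-arm distortion under the literal rule is 0.9(r − c), which is zero when the risks are equal.

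**The case against.** **The routing may never operate.** Most of the protocol's text sends these events to the AE page, and a site following it would record them properly. This stands: the defect is an inconsistency, not a proven loss. But two sites could record the same event differently, so it still needs resolving.

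**Dosed subjects may be counted anyway.** A Day 1 event on the AE page counts if TEAEs are classified by date. SAP 7.3.5 also imputes a missing start date to the index injection date when the event ends on or after that date or is ongoing. This stands for dosed subjects, provided the event reaches the AE page. It does nothing for a subject who received no drug.

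**Undosed subjects do not vanish.** Protocol 3.3.4 asks for follow-up of anyone discontinued after randomisation, and 3.5.5 asks for the reason for any early termination. SAP 7.2.4 lists exclusions from the populations with reasons, 7.5 shows numbers randomised and in the Safety Population, and 7.10 counts who received the index injection. All AEs are listed, and SAEs are reported whatever their relationship to drug. All of this stands. However, a listing is not a comparison between arms, and SAP 7.5 tabulates reasons for early termination on the Safety Population only.

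**The asymmetry is inferred.** The rule covers both arms, and the partly redacted text of Protocol 3.1 appears to place the control injection under fluoroscopic guidance too. Protocol 3.1 does not divide transforaminal events into before and after the drug, and it speaks of interruption, not abandonment. This stands, and it leaves only a plausible direction.

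**The Safety Population is a legitimate choice.** Grouping dosed subjects by treatment received is sound, and adding undosed subjects would dilute post-dose rates. This stands.

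**Some text is not visible.** The Baseline Visit procedures are redacted and the injection instructions in Appendix D are not in the file. Either could add AE instructions, but these would still have to agree with 4.2.1, 5.2.9.1 and SAP 7.2.2.

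**Conclusion.** The point holds as an internal conflict in AE recording combined with a gap in the summary tables. Read literally, the rules leave events with onset during index needle placement out of the TEAE and procedure-related TEAE tables. On any reading, a randomised subject whose procedure stops before any drug is in no AE summary table. Procedure harm with onset after the drug is counted, and a subject given part of the dose is arguably in the Safety Population.

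A reader might infer that these events are certainly lost, that placebo would lose almost none, and that the safety comparison is therefore biased in favour of SP-102. The documents do not support that. They disagree about where the events are recorded, apply the same rule to both arms, and give no rate for pre-dose events or stopped procedures.

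What remains is a directional risk of unknown size. Protocol 3.1 suggests the direction. The ranges of 0.9 to 9.0 points (literal) and 0.09 to 4.26 points (by date) depend entirely on the assumed r, f and q, and the net effect shrinks by whatever the control arm also loses.

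**What to change.** 1. Reconcile the pre-dose sentence in Protocol 4.2.1 with the end of that section and with 3.4.8.1, 3.5.7.6 and 4, so that any AE from the start of the index injection procedure goes on the AE page. Name the step that marks the start.
2. In Protocol 5.2.9.1 and SAP 7.13.1, count AEs with onset at or after the start of the index procedure as treatment-emergent. State whether onset is judged by date or by clock time.
3. Keep the Safety Population as defined. Add one supplementary table, by assigned arm, of AEs and stopped procedures in all randomised subjects whose index procedure was started.
4. In Protocol 3.3.4 and 3.5.5, require the termination page for every randomised subject, in line with the sentence in 3.3.4 on follow-up after randomisation.

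The cost is wording in both documents, one extra table, and a termination page for any undosed subjects. No visits or procedures are added. The SP-102 AE percentage may become slightly less favourable.
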